### **5.5.2. Study Stopping Rules**

The study may be stopped at the discretion of the sponsor or for any reason specified in [Section 3.5](#) Criteria for Study Termination. In all cases, all necessary measures will be taken to ensure appropriate safety follow-up of all participants in the trial.

## **5.6. Concomitant Medications**

### **5.6.1. Prohibited Medications**

The following concomitant therapies are prohibited:

- Use of any prescription or OTC medications, including GLP-1 agonists (e.g., prescribed for weight management), food supplements, vitamins, herbal medications (e.g., St. John's wort), and cannabis, with the exception of contraceptive medications and as needed (prn) acetaminophen (also known as paracetamol) (not exceeding 2 grams/day) within 7 days prior to study drug administration and through the Day 15 visit.
- Any investigational drug or device within 30 days or 5 half-lives of the drug, whichever is the longer, prior to Day 1 and through the Day 15 visit.

If deemed necessary by the Investigator, medications for TEAEs may be administered regardless of relationship to treatment with study drug. All concomitant medications taken in conjunction with a TEAE will be recorded in the source documents and in the eCRF.

### **5.6.2. Contraception**

Individuals of reproductive potential who are (hetero) sexually active must be willing to use effective contraception from Screening through 60 days after the Day 15 visit. (Individuals who are at least 1 year post-menopausal are not of reproductive potential.) Acceptable means of contraception include:

- Individuals who have been surgically sterilized.

- Females of reproductive potential: diaphragm, injectable, oral/patch contraceptives for a minimum of 6 weeks, contraceptive sponge, implant, or intrauterine device in use prior to enrollment, with use of condom for their male partners.
- Males: Males must agree to not donate sperm and to use condom and spermicide in combination with any of the above means of contraception for their female partners during sexual intercourse from the time of the first study drug administration and for 90 days following the last dose of study drug.
- All individuals: abstinence may be an acceptable means of contraception as long as the individual consents to initiate immediate use of double barrier protection for the duration of the study should (hetero) sexual intercourse occur.

### **5.6.3. Restrictions**

Participants must adhere to the following restrictions during study participation:

- Smokers of cigarettes, cigars, cigarillos, or E-cigarettes.
- No alcohol containing foods or beverages; grapefruit-containing foods or beverages; or Seville orange or orange-containing foods or beverage from within 72 hours before the first study drug dose through the Day 15 visit.
- No strenuous activity from 48 hours prior to Day -1 through the last PK sample collection time point.
- No blood product (including plasma) donation within 30 days before Screening through Day 15, the last PK sample collection time point.
- Avoidance of outdoor sun exposure and tanning by consistent use of long sleeve shirts, long pants, hats, and sunglasses and consistent use of SPF 75 or greater sunscreen when outdoors from Study Days 1 through 15.

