**Figure 1: Study Schema**

***Sequence 1***

***Sequence 2***

Participants will be randomized 1:1 into one of two sequences in this comparative, single dose, crossover study.

Participation in the study will be conducted in the following 5 defined periods:

- **Screening Period:** The Screening Period begins upon completion of the informed consent form (ICF). During this period, participants will undergo baseline assessments to determine eligibility

for study participation. The Screening Period duration will be up to 21 days; it will end after all evaluations required to meet eligibility have been completed. If a participant meets all eligibility criteria, they will be offered enrollment into the study.

- **Admission to Study Site:** Participants will be admitted to the study site in the morning on the day prior to dosing of period 1 (Day -1). Participants that are eligible to participate in the study and are randomized into the study will remain at the study site until completion of the treatment period (Study Day 15).
- **Treatment Period:** This study consists of two treatment days separated by a 7-day washout period. The first treatment day will begin on Day 1 of Period 1 with administration of the first dose of study drug. The second treatment day will occur on the first day of Period 2 (Study Day 8). Following the dosing of the study drug on each treatment day, fifteen venous blood samples will be withdrawn via an indwelling cannula or by venipuncture at regular time intervals.
- **End of Active Treatment (Day 15 Discharge Visit or Early Termination (ET) Visit):** Upon successful completion of active treatment, participants will be discharged from the study site on Study Day 15. The Discharge Visit will include the completion of safety assessments, such as a physical examination, vitals, ECG recording, adverse event review, and clinical laboratory tests. Participants who complete both dosing days will be encouraged to complete all study visits. Participants who do not complete all study visits or terminate from the study prior to Day 15 will be asked to complete the Early Termination Visit within 1 day after withdrawal from the study.
- **Day 36 Telephone Follow Up Phone Call:** Participants will be contacted by phone on Day 36—i.e., 28 days following the last study dose administered on Day 8. The purpose of this follow-up call is to assess for any adverse events.

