#### **Study Duration:**

- Total study duration per participant is approximately 57 days:
  - Screening: Approximately 21 days

- Treatment Period: 14 days
- Day 15 Discharge Visit or Early Termination Visit: 1 day
- Day 36 Telephone Follow Up Call: 1 day

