In rats, the 28-day NOAEL was 30 mg/kg. An additional 17-day (females) / 16-day (males) NOAEL of 50 mg/kg were also determined in this study. Based on these NOAEL values, a maximum recommended starting dose (MRSD) of 28.8 (rounded to 30) mg per day was calculated for the initial dose of the Phase 1 study. Target organs histopathologically identified in ARN-75039-treated animals include the bone marrow (rats and dogs), liver (rats), spleen (rats), stomach (rats) and thymus (dogs). As ARN-75039 is an anti-viral with no intended mammalian molecular target, none of the target organ effects noted in ARN 75039-treated animals were considered to be mechanism-related; all target organ effects were considered to be scaffold-related. The results of standard genotoxicity and phototoxicity studies indicate that ARN-75039 does not pose a genotoxic risk but does pose a potential phototoxic risk to humans.

In the GLP dog repeat-dose oral toxicity studies, a 14-day NOAEL of 30 mg was determined. Initially ARN-75039 was administered to Beagle dogs once daily via oral gavage (5 mL/kg) at dosages of 0 (vehicle), 100, 300 and 1000 mg/kg/day beginning on Day 1. However, dose-limiting moribundity was encountered at all doses. Due to unanticipated evidence of dose-limiting moribundity noted during the first week of the dosing phase dogs were given a dosing holiday for 8–10 days and then subsequently administered  $\sim 30\times$  lower doses (at 3, 10, and 30 mg/kg) for the remaining 14 days. All animals completed 14 days of the reduced dosing indicating that any toxic effects were reversible. Following the dose holiday/dose reduction, some ARN-75039-related clinical observations persisted, including diarrhea, emesis, and salivation. The incidence of these observations was greater at the high-dose level relative to mid- and/or low-dose levels, but none of the observations were considered adverse during the Day 15–28 dosing period. ARN-75039-related effects on body weight and food consumption at the lower

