- **End of Active Treatment (Day 15 Discharge Visit or Early Termination Visit):** Upon successful completion of active treatment, participants will be discharged from the study site on Day 15. The Day 15 Discharge Visit will include the completion of safety assessments, such as a physical examination, vitals, ECG recording, adverse event review, and clinical laboratory tests. Participants who complete both dosing days will be encouraged to complete all study visits. Participants who do not complete all study visits or terminate early from the study will be asked to complete the Early Termination Visit within 1 day after withdrawal from the study.
- **Day 36 Telephone Follow Up Phone Call:** Participants will be contacted by phone on Day 36—i.e., 28 days following the last study dose administered on Day 8. The purpose of this follow-up call is to assess for any adverse events.

If a participant has a study drug-related Grade > 1 TEAE during the Treatment Period, study drug dosing may be discontinued for that participant following discussion between the Investigator and Sponsor Medical Monitor. These participants will not be replaced. If a subject has a study drug-related Grade 1 TEAE during the Treatment Period, study drug dosing may also be discontinued for that subject per the Investigator's discretion. However, these subjects may be replaced at the Sponsor's discretion. Discontinued participants experiencing a study drug-related TEAE will be asked to complete follow up study visits through the Day 36 Phone Call Follow Up.

If a participant terminates early for a reason other than a study drug-related TEAE during the Treatment Period, the participant may be replaced. These participants will also be asked to complete follow up study visits through the Day 36 Phone Call Follow Up, unless they terminated their participation in the study prior to dosing. Study drug dose level modifications or dosing administration deviations outside the protocol-specified windows are not permitted during the Treatment Period.

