### 3.2. Justification for the Study Design

A randomized, comparative, crossover study was selected to eliminate participant variation and to improve precision of the PK characteristics of both study drug formulations with a smaller sample size. To compensate for the long half-life of the study drug and the relatively short washout period, additional PK timepoints were included to aid in modeling of the study drug clearance and elimination.

This clinical study is being performed in healthy participants to avoid interference with the results from disease processes and other drugs. Medications, substances, and food products that may interfere with the assessment of the PK profile of ARN-75039 are prohibited during study participation.

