9. Must be willing and able to comply with measures to avoid photosensitivity reactions (i.e., avoidance of outdoor sun exposure and tanning; consistent use of long sleeve shirts, long pants, hats, and sunglasses; consistent use of sun protection factor [SPF] 75 or greater sunscreen when outdoors) during the study treatment period.
10. Able to consume a standard meal (400-600 Calories) within 30 minutes.
11. Able to provide informed consent.
12. Willing and able to comply with this protocol and be available for the entire duration of the study.

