**Table 2: Mean Pharmacokinetics of ARN-75039 100 mg Prototype 1 and Prototype 5 Tablets and HPMC Capsules**

Oral Dose	C max ng/mL	T max (h)	AUC 0-24 (ng/mL*hr)	C min 24 hr ng/mL (μM)	Clearance (mL/min/kg)	Vd (L/kg)
100 mg API Neat in HPMC capsule	4518	5	45453	369.1 (0.89)	4	4
100 mg tablet P1	5105	2	39211	335.6 (0.81)	4	7
100 mg tablet P5	5346	4	42542	399 (0.96)	5	-

Abbreviations: API = active pharmaceutical ingredient; HPMC = hydroxypropyl methylcellulose

Prototype 5 stability after one month at both long-term (25°C/60% RH) and accelerated (40°C/75% RH) stability is presented in [Table 3](#).

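### Sun precautions for the named potential phototoxic risk end on Study Day 15, the discharge day and 7 days after the second dose, with no margin after discharge and no stated reason

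*Protocol*

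**What the plan says.** - **Hazard.** Protocol section 1.2.3 reports from the phototoxicity studies that the drug "does pose a potential phototoxic risk to humans".
- **Precaution and its end.** Section 5.6.3 tells participants to avoid sun and tanning, cover up, and make "consistent use of SPF 75 or greater sunscreen when outdoors from Study Days 1 through 15".
- **Eligibility wording.** Inclusion criterion 9 (section 4.1 and Synopsis) asks for willingness to follow the same measures, in words ending "sunscreen when outdoors) during the study treatment period". The Synopsis lists "Treatment Period: 14 days" under Study Duration, and elsewhere has that period completed on Study Day 15.
- **Dosing and confinement.** Doses fall on Days 1 and 8. Participants are admitted on Day -1, and section 3.1 states that "participants will be discharged from the study site on Day 15".
- **Elimination.** Section 3.2 justifies the added PK time points with the words "To compensate for the long half-life of the study drug and the relatively short washout period". No human half-life is given anywhere in the protocol or SAP.
- **After discharge.** The only planned contact is the Day 36 telephone call, which asks about adverse events.

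**The concern.** An outdoor precaution is useful when people are outdoors. Completers live at the site from Day -1 to Day 15, so the rule is in force for their confinement plus the day they leave. From Day 16 they are back in ordinary daylight with no stated precaution. The second dose is then just over a week behind them, and the protocol itself describes that interval as short relative to the drug's half-life.

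No visible passage links Day 15 to clearance or to photosafety. Day 15 is also the last PK sample and the shared end of the diet, alcohol, medication and blood-donation limits, so it may have been chosen as a convenient common date. Skin signs are monitored as events of special interest (section 6.12.6) and the Day 36 call may pick up a reaction, but detection does not prevent one. At stake is an avoidable skin reaction in healthy volunteers who gain nothing from the drug, 16 of whom are planned.

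**Working it through.** **Inputs from the documents.** Last dose Day 8; end of precautions Day 15; telephone call Day 36; dog PK means in Table 2, section 5.2. **Assumed by this review.** Five half-lives as the yardstick (the protocol uses five half-lives only for prior investigational agents), first-order decline, and a range of human half-lives.

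**1. The plan's interval.** 15 − 8 = 7 days = 168 h. As a check on day counting, 36 − 8 = 28 days, which matches the protocol's own description of the call.

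**2. Half-life at which Day 15 is enough.** 168 / 5 = 33.6 h, or about 34 h. Counting to the end of Day 15 with an assumed 08:00 dose, (168 + 16) / 5 = 36.8 h.

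**3. What the dog data imply.** t½ = 0.693 × Vd / CL.
- Row "100 mg API Neat in HPMC capsule": 0.693 × 4000 / 4 = 693 min = 11.6 h.
- Prototype 1 tablet: 0.693 × 7000 / 4 = 1213 min = 20.2 h.
- Prototype 5 tablet (the one used in this trial): no Vd reported.

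Both values are well below 34 h. They rest on clearances and volumes printed as single digits.

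**4. Range for humans.** End day = 8 + 5 × t½ / 24. Share of the second dose's level left at 168 h = 2^(−168 / t½).

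| Assumed t½ (h) | Five half-lives end on Day | Days beyond Day 15 | Left at 168 h |
|---|---|---|---|
| 12 | 10.5 | 0 | 0.006% |
| 20 | 12.2 | 0 | 0.3% |
| 24 | 13 | 0 | 0.8% |
| 33.6 | 15 | 0 | 3.1% |
| 48 | 18 | 3 | 8.8% |
| 72 | 23 | 8 | 19.8% |

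These shares count the second dose only. Adding what remains of the first dose raises the last two to 9.6% and 23.8%. They also assume decline at the terminal rate from the start. If there is an early, faster fall, the share of peak left at 168 h is smaller.

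**5. An upper limit already in the schedule.** The Day 36 call is 28 × 24 = 672 h after the last dose, and 672 / 5 = 134.4 h. A window ending there covers five half-lives for any t½ up to about 134 h. It adds 36 − 15 = 21 days.

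**The case against.** The strongest reply is that nothing shows Day 15 to be too early. The deciding figures, the human half-life and the exposure at which phototoxicity would occur, are not in the file. The sponsor has human single-dose experience up to 2000 mg (note in section 1.2.3) and refers to the Investigator's Brochure. The only disposition numbers available favour the protocol. In Table 2 the dog level at 24 h is already 369.1 / 4518 = 8.2% of Cmax for the capsule, 335.6 / 5105 = 6.6% for prototype 1 and 399 / 5346 = 7.5% for prototype 5. Section 3.2 concerns carry-over in a crossover, where small residues matter (the SAP acts at 5% of Cmax), and does not discuss photosafety. Completers are also housed for seven days after each dose, which covers peak exposure. All of this stands, and it rules out any claim of demonstrated harm. It does not supply the missing reason or a margin after discharge.

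A reader might infer two stronger points that the documents do not support.

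- **That inclusion 9 materially contradicts section 5.6.3.** Reading the treatment period as 14 days makes a difference of at most one day. Inclusion 9 tests willingness; section 5.6.3 is the operative rule and covers that day. Aligning the wording is tidying.
- **That a late skin reaction would be lost because the SAP counts events as treatment-emergent only to about 7 days after the last dose.** The protocol's own definition (section 6.12.1.5) has no upper limit, and sections 6.12.1.1 and 6.12.4 collect adverse events through the end-of-study visit. The SAP window is a separate matter, and a longer sun precaution would not change it.

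**Conclusion.** The point holds as a small, optional improvement, with moderate confidence. For completers, precautions against a hazard the sponsor names run almost entirely inside confinement and stop with no margin after discharge. The residual risk cannot be quantified from these documents. On the five-half-life convention, the shortfall is zero if the human half-life is about 34 h or less, and 3 or 8 days at assumed values of 48 or 72 h. The dog values (about 12 and 20 h) fall in the zero range but do not settle the human value. The conclusion also assumes that no unseen text, such as consent pages, discharge instructions or the Investigator's Brochure, already extends the precautions or justifies Day 15.

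**What to change.** In section 5.6.3, with matching wording in inclusion 9 (section 4.1 and Synopsis), replace the end with: *through N days after the last dose of study drug*. Set N from the sponsor's human half-life data, for example five half-lives with a minimum of 7 days. Treat the existing Day 36 call (N = 28) as a conservative upper limit. Repeat the instruction at discharge or early termination.

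One detail needs care. A participant who receives only the Day 1 dose is now covered for 15 − 1 = 14 days, so if N is below 14, add that precautions end no earlier than Study Day 15.

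If human data show a half-life of about 34 h or less, Day 15 can stand; one sentence in 5.6.3 saying so would close the point.

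The cost is wording in three places, consent text if it repeats the same end date, and a reminder at discharge. No visit, sample or analysis changes. The downside is up to 21 extra days of sun precautions at home that site staff cannot supervise, and none if Day 15 is retained.

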### **5.7. Treatment Compliance**

Study drug will be administered orally under the supervision of the Investigator or qualified designee. Since study drug will be orally administered, each participant's buccal cavity will be inspected following dosing to ensure consumption of the encapsulated study drug. In terms of compliance, the study center is required to adhere to all applicable laws, regulations and guidelines including, but not limited to, the US Code of Federal Regulations, the International Council for Harmonisation (ICH) of Technical Requirements for Registration of Pharmaceuticals for Human Use, the Health Insurance Portability and Accountability Act of 1996, as well as any applicable local and federal regulations.

### **5.8. Packaging and Labeling**

Study drug will be packaged and labeled in accordance with applicable regulatory requirements. Study drug labels will not bear any statement that is false or misleading in any manner or represents that the study drug is safe or effective for the purposes for which it is being investigated. ARN-75039 will be supplied to the clinical site as both a neat drug substance and with excipients in tablet formulation. The shipment, packaging, and encapsulation of both formulations of the drug substance and the labeling of the study drug prior to administration to participants are detailed in the Pharmacy Manual.

## **5.9. Investigational Product Retention at Study Site**

It is the responsibility of the Investigator to ensure that all drug substance received at the clinical pharmacology unit is inventoried and accounted for by the recording of details pertaining to study drug in an accountability log provided, or otherwise approved by the Sponsor. Study drug accountability will be verified during on-site monitoring visits.

At the end of the study, the study monitor will conduct a final accountability of all drug substance, encapsulated study drug and tablet drug substance. The Sponsor will make a determination at the end of the study if the remaining drug substance is to be destroyed at the site, per the pharmacy's standard operating procedures (SOPs) or shipped to a suitable location specified by the Sponsor.

## **6. STUDY PROCEDURES**

### **6.1. Informed Consent**

Each participant must sign and date the ICF before participating in any study-specific activities. The ICF may be signed prior to the Screening Visit. After the ICF is signed, the participant enters the Screening Period.

All screening evaluations must be completed and reviewed to confirm that potential participants meet all eligibility criteria. The investigator will maintain a screening log to record details of all participants screened and to confirm eligibility or record reasons for screening failure, as applicable.

A complete description of the study is to be presented to each potential participant and signed and dated informed consent is to be obtained before any study specific procedures are performed. A copy of the signed and dated ICF should be provided to the participant.

### **6.2. Medical History**

A complete medical and surgical history along with demographic data will be obtained for all participants during Screening. Data to be recorded in the source document and eCRF include the participant's sex, race, age, and concomitant medication use.

A recent medical history will be obtained on Day -1 upon admittance to the clinic and prior to study drug dosing to assess continued study eligibility and adherence to final inclusion/exclusion criteria. This recent medical history includes a review for changes from Screening as well as a review of the participant's recent medication use.

### **6.3. Physical Examination**

A complete physical examination will be conducted at the time points designated in the schedule of assessments (SOA) ([Table 1](#)). At other designated time points, a partial (symptom-directed) physical examination may be conducted.

- At a minimum, the complete physical examination should include general appearance, skin, HEENT (head, eyes, ears, nose, and throat), neck (including thyroid and nodes), cardiovascular, respiratory, gastrointestinal, and neurological.
- A symptom-directed physical examination will include assessment of any new participant complaints or changes from baseline as clinically indicated.
- Symptom-directed physical examination should be completed 24 hours post-dose.

Changes from baseline in any physical examination findings identified by the Investigator as clinically significant must be recorded as an AE on the appropriate eCRF.

